APPENDIX 1. DATA COLLECTION FORM

"Implementation of Mandatory Hiataloplasty in Sleeve Gastrectomy: Strategy for Gastro-Esophageal Reflux Disease (GERD) Risk Reduction."

Identification sheet

ID: _____ **Fecha:** _____
Name: _____ **Gender:** : M F Other **Age:** _____
 years.
Teléfono: _____ **Email:** _____
Marital Status: Single Married Divorced Common-law
Country of residence: Mexico USA Other: _____
Nationality: Mexico USA Other: _____
Occupation: _____
Attending Physician: [name] [name]: _____
Planned Surgery: Sleeve Y-Roux SADIS/SD Mini-Gastric Bypass (MGB)
 Rev Sleeve Band Rev Bypass Other: _____
Planned surgery date: _____
Size: _____ meters **Weight:** _____ (before diet): _____ kg **IMC:** _____ : _____
HR: _____ bpm **FR:** _____ rpm **BP:** _____ mmHg **T:** _____ °C

Background

Allergies: Denied Penicillin Sulfonamides AAS

Otro: _____

Smoking: Denied Active Inactive Inactive time (years): _____

Cigarettes per week: _____

Years: _____

Alcoholism: Denied Active Inactive

Social / Drinks per week: _____

Years: _____

Toxicomania: Denied Active Inactive

Type of drug used: Marijuana Cocaine Ecstasy LSD

Heroin Fentanyl Other: _____ Years: _____

Previous hospitalizations: denied Yes How long ago? _____

Motivo:

Blood type: A B AB O

Previous transfusions: denied Yes How long ago? _____

Motivo:

Heredofamiliares

Diabetes: Denied Father Mother Grandparents Siblings Children

Hypertension: Denied Father Mother Grandparents Siblings Children

Cardiac: Denied Father Mother Grandparents Siblings Sons Sons.

Cancer: Denied Father Mother Grandparents Siblings Children Psychiatric: Denied

Father Mother Grandparents Siblings Children Endocrine: Denied Father Mother

Grandparents Siblings Children

Personal

Diabetes: No Yes Time of evolution: _____ years Are you in control? No Yes

Treatment used:

No treatment Insulin: _____ IU/day.

Metformin: _____ mg/day Hypoglycemic: _____

Other: _____

Arterial Hypertension: No Yes **Time of evolution:** _____ years **Is it under control?** No Yes

Treatment used:

 No treatment	 ACEI: _____
 ARA 2: _____	 BetaBlocker: _____
 Ca Antagonist: _____	 Diuretic: _____

Other Cardiovascular Diseases: No Yes

Enfermedad(es): _____

Time of evolution: _____ years

Treatment used: _____

Cancer: No Yes In recurrence

Type of cancer: _____

Time of evolution: _____ years

Treatment used: _____

Psychological/Psychiatric Illnesses: No Yes

Enfermedad(es): _____

Time of evolution: _____ years

Treatment used: _____

Endocrine Diseases: No Yes

Enfermedad(es): _____

Time of evolution: _____ years

Treatment used: _____

GERD: No Yes

How was the diagnosis made?

Not performed Endoscopy SEGD Phmetry Other: _____

Treatment:

 IBP: _____
 Antacids: _____
 H2RA: _____
 Otro: _____

Previous abdominal surgeries: No Yes

Hernioplasty How many years ago?: _____

BariatricSleeve Y-Roux MGB Band Gastric balloon
Otra: _____

Caesarean section How many: How many years ago (last):

Other: _____

Nausea (that required medication) or vomiting in previous surgeries? No Yes No No Yes

Respiratory symptoms: Denied Rhinorrhea S Dyspnea Cough

Other: _____

Sleep apnea (STOP-BANG):

Do you have loud snoring (heard from another room): Yes No Yes No
Yes No No

Do you feel tired during the day: Yes No
Have you ever been told if you pause your breathing while sleeping: Yes No Yes

No Yes No No

Collar diameter >40 cm: Yes No

Current condition and physical examination

Current condition and physical examination

Current condition and physical examination

Current condition and time of evolution: _____

Previous nutritional treatment: No Yes Which one :

Previous medical treatment: no yes which one :

Neurológico

Conscientious: Yes No **Orientated:** Yes No **Cooperative:** Yes No

Musculoskeletal:

Mobility: Normal Limited None **Muscle tone:** Preserved Altered

Skin and adnexa

Hydration: Good Fair Poor

Coloration: Normal Pallor Icteric Other: _____

Head and neck

Symmetrical: Yes No **Palpable masses:** No Yes

Chest

Cardiac: Normal Murmur Arrhythmia Frémito Other: _____

Pulmonary: Normal Wheezing Rales Rales Other: _____

Abdomen

Pain: No Yes Superficial Deep **Location:** _____

Palpable masses: No Yes Location : _____

Previous incisions: No Yes Type/Location : _____

Megaliths: No Liver Spleen Other: _____

Hernias: No Umbilical Inguinal Other: _____

Extremities: Intact: No Yes Edema: No Yes

Capillary filling: Normal Abnormal

Pre-surgical

Date of surgery: _____**Wearing of TED stockings:** No Yes **Was electrolyte and carbohydrate loading performed at 2 hrs prior to surgery:** No Yes **Pre-operative diet:** No Yes How many days: 1-3 4-7 8-14 >15 **Did you lose weight?** No Yes How many g/kg did you lose:**Pre-surgical weight (after diet):** _____ kg**Laboratories:**

Hb _____ mg/dl

Hto _____

Platelets _____ miles

Leukocytes _____ miles

Glucose _____ mg/dl

HbA1c:

% Urea _____ mg/dl

Creatinine _____ mg/dl

TP _____ sec

TPT _____ sec

INR _____

TGO _____

TGP _____

Total cholesterol _____ mg/dl Triglycerides _____ mg/dl

Previous studies:**TAC:** No Yes Result: _____**USG:** No Yes Result: _____**Endoscopy:** No Yes Result: _____**BP figures:** _____ mmHg **Capillary glucose figures (if diabetic[a]):** _____ mg/dl

Anesthesia

ASA classification: I II III IV V VI **Use of general anesthesia:** No Yes **Antibiotic prophylaxis:** No Yes **Antibiotic used:** Ceftriaxone Levofloxacin Cefazolin Ciprofloxacin

Otro: _____

Antithrombotic prophylaxis: None Enoxaparin Rivaroxaban Acetylsalicylic acid

Otro: _____

Antiemetic prophylaxis: None Ondansetron Metoclopramide Domperidone

Corticosteroid: _____ Other: _____

Use of opioids: none Fentanyl Morphine Tramadol Methadone Nalbuphine

Buprenorphine Oxycodone Other: _____

Use of blood products: No Yes Number _____ **of packages:** _____

Type of blood products: Blood Platelets Plasma

Complications related to anesthesia: No Yes

Which _____ **one(s):** _____

How was it resolved? _____

Transsurgical

Surgery Performed: Sleeve Y-Roux SADIS/SD MGB Band Rev Bypass

Rev Sleeve Other: _____

Stapler type: Manual Electric Other: _____

Number of cartridges (staples) used: _____

Type of cartridges (staples) used: White Blue Yellow Green Black

*Contest as applicable

Probe size used: _____ Fr **Common handle size** : _____ cm

Pouch size: _____ cm **Biliopancreatic loop size** : _____ cm

Food handle size: _____ cm

If MGB, was the gastric remnant resected (Modified Mini Bypass): No Yes

Grapevine line reinforcement: No Invaginating Transcriptional

Sutures used: Prolene Monocryl PDS Other: _____

Was a tightness test performed: No Yes

Gap Closure: No Yes

Suture type: Prolene Ethibond Monocryl PDS Other: _____

Port (trocar) closure: No Yes

Use of sealants (glue): No Yes

Use of drainage: No Yes **Type of drainage:** Open Closed Other: _____

Total operative time: _____ min **Total bleeding:** _____ ml

Patient's final status: Stable Delicate Serious Finished

Trans-surgical complications: None

Bleeding: No Yes **Amount:** _____ ml

Adjacent organ injury: No Yes **Injured organ:** _____

Failure to grapple: No Yes

Otra: _____

How was it resolved? _____

Post-surgical 24 hrs

Early wandering (<6 hrs): No Yes

Nausea that required medication during the first 24 hrs: No Yes

Use of antiemetics: no Ondansetron Metoclopramide Domperidone

Corticosteroid Other: _____

Pain that required medication during the first 24 hrs: No Yes No Yes No

Use of analgesics: Ketorolac Paracetamol Lysine Clonixinate

Metamizole Diclofenac Ketoprofen Parecoxib Ibuprofen

Otro: _____

Opioid use (24 hrs): None Morphine Tramadol Methadone

Nalbuphine Buprenorphine Oxycodone Fentanyl

Otro: _____

Use of antibiotics: No Ceftriaxone Levofloxacin Cefazolin Ciprofloxacin

Ampicillin Clindamycin Other: _____

Drainage output (24 hrs): _____ cc **Characteristics:** Hemic Serohaematic Serous Biliary

Intestinal Other: _____

Was there a need for surgical reintervention: No Yes : No : Yes : No

Motivo: _____

Blood pressure (24 hr): _____ mmHg **Capillary glucose (24 hr):** _____ mg/dl

In-hospital follow-up

At how many hours post surgery did you mobilize: 2-5 6-12 12-24 >24

Did you perform breathing exercises (min 3 times a day): No Yes

How many hours after surgery was the enteral line resumed?

How many days post-surgery was the drain removed?: _____

Did you perform barium swallow test: No Yes **Result:** Normal Leakage

Days of in-hospital stay: _____

Antithrombotic prophylaxis scheme at discharge: None Enoxaparin Rivaroxaban

Apixaban Other: _____

Otro: _____

Need for surgical reintervention prior to discharge: No Yes

Motivo: _____

BP figures (at discharge): _____

mmHgCapillary glucose figures (at discharge):

_____ mg/dl

Respiratory complications

SatO2 (ambient): _____

None Atelectasis: No Yes **Pneumothorax:** No Yes

Venous thromboembolism/VTE: No Deep Venous Thrombosis PET

Other:

_____ **Did**
you require supplemental O2: No Yes **SatO2 (supplemental):** _____

How was it resolved? _____

Other complications

Leakage:	 No  Yes  Urinary	Retention:	:
 No  Yes 			
Dysphagia:	 No  Yes	 Liver	dysfunction :
 No  Yes  Hemorrhage:		 No  Yes  Constipation	:
 No  Yes  Infection:		 No  Yes  Pancreatitis:	
 No  Yes  Intestinal	obstruction:	 No  Yes  Diarrhea	:
 No  Yes  Diarrhea	:	 No  Yes 	
Renal insufficiency:	 No  Yes  No  No  Yes  No		

How was it resolved? _____

Complications according to Clavien-Dindo Classification:

***Classify according to the need for the use of the following medications, interventions and/or occurrence of complications in the patient's hospital course (one or more options, not necessarily all, e.g., a normal post-surgical course is classified as 1 as the use of solutions and analgesics is necessary).**

- 1. Use of solutions, antiemetics, analgesics, antipyretics, need for physiotherapy.
- 2. Use of drugs other than above, blood products, parenteral nutrition.
- 3a. Surgical, endoscopic or radiological re-intervention without the use of general anesthesia.
- 3b. Surgical, endoscopic or radiological re-intervention with use of general anesthesia.
- 4a. Single organ dysfunction (dialysis included).
- 4b. Multiple organ dysfunction.
- 5. Death.

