To evaluate the efficacy of mandatory hiatal hernia repair (hiatoplasty) performed during gastric sleeve surgery in reducing the incidence of postoperative gastroesophageal reflux disease (GERD) in patients undergoing this procedure in a hospital specializing in bariatric surgery in Tijuana, Baja California.

Specific

Demographic characteristics and comorbidities in patients undergoing gastric sleeve with hiatoplasty: These patients usually have significant obesity, often accompanied by comorbidities such as type 2 diabetes, hypertension, sleep apnea, and gastroesophageal reflux disease (GERD). Demographic characteristics may vary, but the prevalence of obesity and its associated comorbidities is high in many regions, including Tijuana, Baja California.

Incidence of postoperative GERD in patients undergoing gastric sleeve with mandatory hiatoplasty: Hiatal hernia repair is often performed to reduce the risk of postoperative GERD by repairing a herniated hiatus during gastric sleeve surgery. However, the exact incidence of postoperative GERD can vary and depends on factors such as surgical technique, patient anatomy and postoperative management.

Comparison of postoperative complication rates, including GERD: Postoperative complications may include, but are not limited to, bleeding, infection, sleeve stenosis, and GERD recurrence. Comparison of complication rates between patients with and without mandatory hiatal hernia repair may provide insight into the effectiveness of this technique in mitigating specific risks.

Postoperative quality of life analysis: Postoperative quality of life can be significantly improved after bariatric surgery due to weight loss and improvement of comorbidities. Specific measures may include, but are not limited to, physical mobility, self-esteem, relief of symptoms of comorbidities, and overall satisfaction with the results of surgery.

Evaluation of the safety and technical feasibility of mandatory hiatoplasty: The integration of hiatal hernia repair into gastric sleeve surgery should be evaluated in terms of technical feasibility, safety, and effectiveness in preventing recurrence of hiatal hernias and GERD. This may involve analysis of complication rates, specific surgical techniques, and long-term.

MATERIALS AND METHODS

Research design

A retrospective case series will be performed.

Universe of study

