Variable	Conceptual definition	Operational definition	Measurement units	Type of Variable
Age	Years a person has lived since birth	Patient's age, recorded in the file.	Years	Quantitative
Sex	Difference in physical and sexual characteristics that distinguish men from women.	Classification of the patient as male or female	Male Female	Qualitative Nominal
Chronic comorbidities	Long-standing diseases directly related to obesity	Additional diseases recorded in the patient's record	None Diabetes mellitus Hypertension Cardiovascular GERD Dyslipidemia Hypothyroidism SAOS Depression Another	Qualitative Nominal
BMI	Universal unit for estimating the amount of body fat a person has.	BMI value recorded in the file, or calculated from weight and height, as: Weight (Kg)/ Size (m) ²	Kg/m ²	Continuous quantitative
Obesity level	Excess or a general excessive accumulation of fat in the body	Degree or level of obesity in the patient. Grade I: 30-34.9 Kg/m ² Grade II: 35-39.9 Kg/m ² Grade III: >=40 Kg/m ² Superobesity >50 Kg/m ² Super-super-obesity >60 Kg/m ²	I II III Superobesity Super-super-obesity	Qualitative ordinal
Duration of surgery	Time of the surgical process.	Time of surgery recorded in the file	Minutes	Quantitative
Trans-operative complications	Adverse events developed during surgery	Perioperative complications recorded in the record	None Bleeding Pneumothorax Organ injury Vascular injury Other	Qualitative Nominal
Postoperative complications	Adverse events developed after surgery	Postoperative complications recorded in the record or mentioned by the patient at follow-up	None GERD Bleeding Leakage Obstruction Diarrhea Embolism Other	Qualitative Nominal

STATISTICAL ANALYSIS

A database will be created in Excel, which will be downloaded into the statistical package SPSS v.26 in its MacOS version for data processing.

A descriptive analysis will be performed. For qualitative variables with frequencies and percentages. For quantitative variables, the descriptive analysis will consist of mean and standard deviation. In case quantitative variables have a non-parametric distribution, median and interquartile range will be used as descriptive statistics.

ETHICAL CONSIDERATIONS

The present research project was submitted to evaluation by the Local Health Research and Bioethics Committees for assessment and acceptance.

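### The Clavien-Dindo item in Appendix 1 grades a normal postoperative course as 1 and has no level for no complication, so its any-grade and grade 1-2 summaries are not complication rates

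*Protocol*

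**What the plan says.** Appendix 1 of the protocol, the data collection form, ends with a Clavien-Dindo item under a complications heading. The basis of grading is broad: "Classify according to the need for the use of the following medications, interventions and/or occurrence of complications in the patient's hospital course". The abstractor may tick more than one option. The form then gives an example: "a normal post-surgical course is classified as 1 as the use of solutions and analgesics is necessary".

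The lowest option printed is "1. Use of solutions, antiemetics, analgesics, antipyretics, need for physiotherapy" and the next is "2. Use of drugs other than above, blood products, parenteral nutrition". Grades 3a to 5 need a re-intervention, organ dysfunction or death. There is no grade 0 and no None.

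The same form records antibiotic and antithrombotic prophylaxis in its Anesthesia section, antibiotics in the first 24 hours, and, under in-hospital follow-up, "Antithrombotic prophylaxis scheme at discharge: None Enoxaparin Rivaroxaban" among other choices.

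In the protocol's table of study variables, postoperative complications are defined conceptually as "Adverse events developed after surgery". They are coded as a list of named events that begins with None. The specific objectives include a comparison of complication rates and an evaluation of safety, of which the protocol says: "This may involve analysis of complication rates, specific surgical techniques, and long-term". The Statistical Analysis section plans frequencies and percentages for qualitative variables.

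**The concern.** A complication grade should separate patients who had an adverse event from those who did not, and then rank the events. This item does neither at its lower end. A normal recovery and a minor event treated with analgesics both become grade 1. A drug given to prevent an event and a drug given to treat one both become grade 2.

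The planned analysis tabulates frequencies and percentages. If this item were tabulated like the other categorical fields, a reader would see a row labelled as complications that covers every patient, next to a postoperative complication variable in which many patients are None. Nothing in the protocol warns that the two are coded on different principles.

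**Working it through.** The protocol states no complication rate, so there is no figure to reproduce. The check is to apply the printed rule to one uneventful patient and compare the result with the variable table.

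**Inputs.** The grading rule, the option list and the prophylaxis fields are from Appendix 1. The coding of postoperative complications is from the table of study variables. The planned minimum of 275 patients is from the Sample size section and serves only as a denominator.

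**Uneventful patient given fluids and analgesics**

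| Source | Code |
|---|---|
| Table of study variables, postoperative complications | None |
| Appendix 1, Clavien-Dindo item | Grade 1, by explicit instruction |

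Leaving the item blank is not a way out, because the instruction assigns the grade.

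**The same patient, also given an antibiotic or an antithrombotic in hospital.** These drugs are not in the grade 1 list, so the literal code is grade 2. The variable table still says None.

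**Any-grade share.** Every patient is either uneventful (grade 1 or 2 by the rule) or has an event (grade 1 or higher). The share is therefore 275/275 = 100%, whatever the true rate.

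**Grade 2 share.** Read literally, it includes every patient given in-hospital prophylaxis. The protocol does not give that share, so the inflation lies somewhere between 0 and 100% of the uneventful patients and cannot be narrowed from the document.

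**Size of the disagreement.** If x of 275 patients are coded other than None in the variable table, the two fields disagree for 275 − x patients. The values of x below are assumptions. The intervals are exact (Clopper-Pearson) 95% intervals for x/275.

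| Assumed x | Named-event rate (95% CI) | Any grade from the item | None in the table but graded on the form |
|---|---|---|---|
| 3 | 1.1% (0.2 to 3.2) | 100% | 272 |
| 14 | 5.1% (2.8 to 8.4) | 100% | 261 |
| 28 | 10.2% (6.9 to 14.4) | 100% | 247 |
| 55 | 20.0% (15.4 to 25.2) | 100% | 220 |

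The named-event rate varies with the data and can be estimated; the any-grade rate cannot vary.

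**What is untouched.** A normal course does not trigger grade 3a or higher. Named complications are also recorded on the form as separate yes/no fields, with space for how they were resolved and fields for re-intervention.

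**The case against.** The strongest reply is that nothing in the protocol uses this grade. It is absent from the table of study variables, from the list of data to be extracted, from the objectives and from the Statistical Analysis section. Appendix 1 is a broad bariatric record, and many of its fields are not study variables. The complication variables that are defined have a None level and are sound. This stands, and it limits the point. A reader might infer that the safety rate means nothing or that the safety objective cannot be answered. The protocol does not support either inference, because no section takes the safety rate from this item, and the named-event rates and grade 3a or higher remain interpretable.

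A second reply is that the two fields measure different things: one grades the hospital course by the care needed, the other lists events from the record or from follow-up. This is partly right. But the item sits under a complications heading and carries the name of a complication scale, so its numbers would be read as complications.

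A third reply concerns grade 2. The protocol does not call prophylaxis routine, each field allows None or No, and the antibiotic field for the first 24 hours is not labelled prophylaxis. The form's own example puts a normal course at 1, which suggests that usual care was not meant to reach 2. This stands against any figure for the inflation. It does not remove the ambiguity, since the grade 2 text has no exception and two abstractors could code the same patient differently.

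Two smaller replies also stand. Multiple ticks do no harm if the highest is used, although the form does not say so. Minor events are not lost from the form as a whole, because the yes/no fields keep them. They are lost only within grades 1 and 2 of this item.

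A statistical analysis plan that is not shown could leave the item out of the tables. It would not correct the coding rule, which is fixed in the protocol.

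**Conclusion.** Wrong as written, minor. The Clavien-Dindo item assigns a grade to every patient, so its any-grade share is 100% by construction and its grade 1-2 counts mix routine care with minor events. Neither can be read as a complication rate, and both conflict with the postoperative complication variable, where an uneventful patient is None.

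The 100% follows from the printed instruction alone and needs no assumption about event rates. It assumes only that abstractors follow the form. The grade 2 inflation is real on a literal reading but cannot be sized. The conclusion does not extend to the named-event rates, to grades 3a and higher, or to the safety objective as a whole.

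**What to change.** Change the item in Appendix 1 as follows:

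- Add a level for None (no complication).
- Delete the instruction that grades a normal course as 1.
- State that a grade is assigned only when an adverse event is recorded, and that expected fluids, analgesia and prophylaxis do not count towards it.
- Keep one value per patient, the highest grade.

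For records already abstracted, set the grade to None where all the yes/no complication fields on the form are negative. Regrade the remainder from those fields and from the entries on resolution and re-intervention. If this cannot be done reliably, report only grade 3a or higher from this item, alongside the named-event rates from the variable table.

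The cost is the rewording of one form item and a recoding pass over data already collected. No new data are needed, and the sample size and planned descriptive analysis do not change.

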APPENDIX 2. FOLLOW-UP FORMAT

Follow Up Questionnaire

Please answer the following questions based on the present or how you currently feel

Weight *

Texto de respuesta corta

Did you describe your weight in kilograms or pounds? *

- Kg
- Lbs

Please select the checkboxes that best describes your current conditions (if any) compared to before your surgery

If you don't have any medical conditions, please skip this question

	Aggravated	Unchanged	Improved	Resolved
Diabetes				
Hypertension				
Dyslipidemia				
Apnea				
Depression				
Anxiety				
Reflux				
Insomnia				

If you were taking medications, has there been any change in your medication consumption after your surgery? *

- I did not take any medication
- Yes, now I take a lower dosage and/or less medications
- No, there were no changes
- Yes, now I take a higher dosage and/or more medications

Please specify the medications and dosages you are currently taking

Texto de respuesta larga

Do you suffer from frequent diarrhea? *

- No
- Yes

Does your diarrhea require medication?

- No
- Yes

Do you have very foul-smelling flatulence? *

- No
- Rarely
- Occasionally
- Frequently

Do you have very foul-smelling stools? *

- No
- Rarely
- Occasionally
- Frequently

Have you suffered any fractures after your bariatric surgery? *

- No
- Yes

Where on your body and in what year did the fracture occur?

Texto de respuesta larga

Have you ever been told that you have thinner bones or osteoporosis? *

- No
- Yes

Quality of Life

Please answer the following questions based on how you currently feel

Usually, I feel... *

1 2 3 4 5

Very bad about myself

Very good about myself

I enjoy physical activities... *

1 2 3 4 5

Nothing at all

Very Much

I feel comfortable in social gatherings... *

1 2 3 4 5

Nothing at all

Very Much

I am able to work... *

1 2 3 4 5

Nothing at all

Very Much

The pleasure I get out of sex is... *

1 2 3 4 5

Nothing at all

Very Much

Reflux Scale

Please answer the following questions based on how you currently feel

How bad is your heartburn? *

Heartburn when lying down? *

Heartburn when standing up? *

Heartburn after meals? *

Does heartburn change your diet? *

Does heartburn wake you from sleep? *

Do you have difficulty swallowing? *

Do you have pain with swallowing? *

Do you have bloating or gassy feelings? *

Do you have bloating or gassy feelings? *

If you take medications, does this affect your daily life? *

How satisfied are you with your present condition? *

- Satisfied
- Neutral
- Dissatisfied
